4.3 JUSTIFICATION FOR DOSE

Not applicable

4.4 END OF STUDY DEFINITION

A provider participant is considered to have completed the study if they have completed the intervention period as shown in the Schedule of Activities (SoA), Section 1.3 or they leave employment at HealthPartners. A provider participant will have the option to provide feedback about their experience during the intervention period in a sub-study evaluating the intervention.

For a patient not selected to complete a survey, they are considered to have completed the study when regular dental care for their index extraction encounter is completed as shown in the Schedule of Activities (SoA), Section 1.3.

For a patient participant selected to complete a survey, they are considered to have completed the study after completing the survey call as shown in the Schedule of Activities (SoA), Section 1.3.

The end of the study is defined as completion of the last procedure shown in the SoA in the trial globally.

5 STUDY POPULATION

5.1 INCLUSION CRITERIA

Providers

In order to be eligible to participate in this study, an individual must meet all of the following criteria:

- Have a current Drug Enforcement Administration (DEA) number allowing them to write prescriptions for controlled substances, including opioids, during the baseline period
- Perform dental extractions of permanent teeth on a regular basis (a minimum of 6 extraction encounters during the baseline period)

Patients

In order to be eligible to participate in this study, an individual must meet all of the following criteria:

- Have a dental extraction of a permanent teeth performed by an eligible HealthPartners provider during the intervention period

5.2 EXCLUSION CRITERIA

Patients

An individual who meets any of the following criteria will be excluded from participation in this study:

1. Patients who have opted out of research at HealthPartners
2. Patients under 16 years of age

5.3 LIFESTYLE CONSIDERATIONS

Not applicable

5.4 SCREEN FAILURES

Implementation of the CDS is considered a HealthPartners Dental Group initiative in as a part of their strategy to reduce opioid prescribing. As such, providers are not consented for the study. Providers not eligible for the study will not be included in data collection activities and the data from their patients will not be included in the study. There will be no screen failures for providers.

Patients will not be consented to the study for the primary study objective. Patients not eligible for the study or those who have opted out of research will not be included in the analysis. Patients who provide consent for the survey-based objective are known to be study eligible at the time their consent is requested. There will be no screen failures for patients.

5.5 STRATEGIES FOR RECRUITMENT AND RETENTION

Implementation of the CDS is considered a HealthPartners Dental Group initiative. The project is being implemented with the aim of reducing opioid prescribing. Consent has been provided by dental leadership in accordance with HealthPartners practices.

Providers randomized to the CDS or CDS-E will be exposed to the clinical decision support, integrated into the EHR. Patients who receive care from providers randomized to the CDS-E arm will also be exposed to study-specific patient education.

For the subset of patients eligible to receive a survey, patients will provide verbal consent for survey participation via telephone, which will be obtained by trained survey administrators. If a patient chooses not to participate, another patient will be sampled and called.

Further information about the strategies for recruitment and retention are detailed in the Manual of Procedures.

6 STUDY INTERVENTION

6.1 STUDY INTERVENTION(S) ADMINISTRATION

6.1.1 STUDY INTERVENTION DESCRIPTION

The study intervention will be active within HealthPartners Dental Group for 12 months or until patient accrual goals are met. After completion of the study, the HealthPartners Dental Group will decide whether to continue its activity, but this will be beyond the study's scope.

Standard Practice: Providers will not receive point of care decision support, serving as the control group representing usual care. Patients will receive usual dental care.

CDS: Providers will receive point of care decision support to guide pain management recommendations and prescribing for patients who receive dental extractions. The clinical decision support will highlight: (1) potential medication interactions between the patient's current medications and commonly recommended analgesics for patients following dental extractions; (2) relevant health conditions that may impact pain management strategies; and (3) automated access to the Prescription Drug Monitoring Program. Patients will receive usual dental care [when implemented by HealthPartners Dental Group: access to the Prescription Drug Monitoring Program via the clinical decision support tool will be suspended to align with the organization approach via the electronic health record].

CDS-E: Providers will receive point of care decision support to guide pain management recommendations and prescribing related to dental extractions. The clinical decision support will highlight: (1) potential medication interactions between the patient's current medications and commonly recommended analgesics for patients following dental extractions; (2) relevant health conditions that may impact pain management strategies; and (3) automated access to the Prescription Drug Monitoring Program [when implemented by HealthPartners Dental Group: access to the Prescription Drug Monitoring Program via the clinical decision support tool will be suspended to align with the organization approach via the electronic health record].

In addition, patients will receive an educational handout prior to the extraction procedure comparing effectiveness for managing pain, risks and benefits of non-opioid pain medications and opioid medications. This handout intends to initiate a conversation between the patient and provider about patient needs, goals and preferences. The patient will also receive an education handout about pain management after dental extraction for their reference. This handout intends to normalize the experience of some discomfort and to help patients decide about whether to contact their provider for additional help to manage their pain after extraction. Patients will receive usual dental care.

6.1.2 DOSING AND ADMINISTRATION

Not applicable

6.2 PREPARATION/HANDLING/STORAGE/ACCOUNTABILITY

Not applicable

6.3 MEASURES TO MINIMIZE BIAS: RANDOMIZATION AND BLINDING

The randomization of providers to study arm will utilize stratification on baseline factors in order to balance key provider factors evenly across study arms. Specific stratification factors to be utilized will be outlined in the Statistical Analysis Plan. Providers will be randomly allocated 1:1:1 through a computer-generated program to either Standard Practice, CDS, or CDS-E. Patients will be exposed to the intervention to which their provider has been randomized based on the provider they see at the index extraction visit. Systematic sampling with a variable sampling ratio by provider will be used to identify a sample of patients to receive the post-visit survey. This sampling strategy will approximate stratified random sampling and ensure roughly equal counts of patient surveys by provider and study arm. At each patient encounter, the CDS Web service will collect patient level data from the EHR (e.g., medical conditions, current medications, social history). Providers assigned to the CDS or CDS-E arms will be able to access the information using the CDS tool. Providers assigned to the control arm will continue to use their usual methods to assess and address pain management for dental procedures without any effort to influence their prescribing of analgesics following the dental extraction. They will not be shielded from other outside influences.

At the index encounter (the initial patient visit for a dental extraction during the intervention period where all the study criteria are met), the patient is assigned a unique study identifier that is used to link patient encounter data over time. All index and subsequent encounter data for eligible patients are stored in a limited de-identified analysis dataset.

In order to minimize contamination across study arms, only providers in the CDS or CDS-E arms will be able to access the clinical decision support. Similarly, patients who receive care from providers in the CDS-E arm will have access to supplemental patient education. As such, both groups will know their assignment. The study team will not disclose the study's purpose, objectives, or outcomes measures directly to patients until after the encounter or after the participant has been surveyed about their experience, if selected.

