9.4 STATISTICAL ANALYSES

9.4.1 GENERAL APPROACH

Baseline characteristics of study participants will be summarized with mean and standard deviation for interval data and proportions for categorical data. General and generalized linear mixed models will be used to test study arm differences in endpoints. Models will include terms for study arm, time (for models assessing change from pre- to post-intervention), and their interaction. Covariates to be included in models will be described in the Manual of Procedures (MOP). A random intercept for provider will be included in models to account for the cluster-randomized design with providers as the unit randomized. Differential change will be compared for each study arm via a series of planned contrasts. Study arm contrasts will be tested at alpha=0.05 and all tests will be two-sided. Model-predicted means and proportions along with 95% confidence intervals will be used to assess the magnitude, direction, and precision of intervention effects.

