9.4.2 ANALYSIS OF THE PRIMARY EFFICACY ENDPOINT(S)

H1: Providers in the CDS and CDS-E strategy arms will reduce their likelihood of prescribing opioids for patients following extractions more than providers in the SP arm.

Analysis plan: Hypothesis H1a posits that patient encounters at which extractions are performed by dental providers in the CDS and CDS-E arms will have a larger reduction in the likelihood of receiving an opioid prescription at the index encounter than patient encounters in the SP arm when comparing independent samples of patient encounters before the implementation to patient encounters following the implementation. A generalized linear mixed-model regression with a logit link and binomial error distribution will be used to test the effects of the implementation strategies. The patient-level endpoint (patient received an opioid prescription at the index encounter) is coded as a binary outcome variable. This endpoint will be predicted by 2 fixed-effects terms for study arm of CDS (CDS vs. SP) and CDS-E (CDS-E vs. SP), year in which the patient has an extraction (post or pre-implementation), and by interaction terms of study arm and year. A random intercept for provider will be included in the model to accommodate the cluster-randomized design with providers as the unit randomized. Additional covariates to be included will be described in the MOP. Model-predicted proportions and confidence intervals of opioid prescribing will be summarized by time and study arm jointly. Contrasts will estimate differential reduction in the endpoint comparing CDS vs. SP and CDS-e vs. SP. This analysis will be conducted on the Intention to Treat Analysis Dataset.

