9.4.3 ANALYSIS OF THE SECONDARY ENDPOINT(S)

H2: Providers in the CDS and CDS-E strategy arms will increase their likelihood of satisfying the composite endpoint defined by: 1) prescribing or recommending non-opioid analgesics at the extraction encounter and 2) not prescribing opioids at the index encounter for patients following extractions more than providers in the SP arm.

Analysis plan: Hypothesis H2 posits that patient encounters at which extractions are performed by dental providers in the CDS and CDS-E arms will have a larger increase in the likelihood of receiving a prescription or recommendation for non-opioid analgesics and not prescribing opioids at the index encounter than patient encounters in the SP arm when comparing independent samples of patient encounters before the implementation to patient encounters following the implementation. The same analytic strategy used for the primary endpoint will be used for this secondary endpoint and will be conducted on the Intention to Treat Analysis Dataset.

H3 (alternative): Patients will report higher levels of the extent of shared decision making in the CDS-E arm than the CDS or SP arms.

Analysis plan: Hypothesis H3 posits that patients will report higher levels of the extent of shared decision making in the CDS-e arm than CDS or SP arms during the strategies implementation time period. A general linear mixed-model regression with an identity link and normal error distribution will be used to test the effects of the implementation strategies. The patient-level endpoint is the score on the 3-item composite of adapted Collaborate Shared Decision Making, and is considered an interval-level variable. This endpoint will be predicted by 2 fixed-effects terms for study arm of CDS (CDS vs. SP) and CDS-E (CDS-E vs. SP). A random intercept for provider will be included in the model. Additional covariates to be included will be described in the MOP. Model-predicted means and confidence intervals for the endpoint will be summarized by study arm. A contrast will estimate the difference in the mean of the endpoint for patients in the CDS-e arm vs. CDS and SP (pooled). This analysis will be conducted on the Intention to Treat Analysis Dataset.

H4 (descriptive): Compare patient report of mean pain in the week following tooth extraction across the 3 study arms.

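### Providers are randomised within strata, but no model is committed to the stratification factors; if they are left out, the H3 and H4 standard errors come out too large

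*Combined protocol and SAP*

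**What the plan says.** Section 6.3 plans stratified allocation of providers, "The randomization of providers to study arm will utilize stratification on baseline factors", and adds that "Providers will be randomly allocated 1:1:1 through a computer-generated program" to the three arms. At the target of 51 providers this gives 17 per arm. The factors are not named there: "Specific stratification factors to be utilized will be outlined in the Statistical Analysis Plan".

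Section 9.4.1 sets the common model structure: "Models will include terms for study arm, time (for models assessing change from pre- to post-intervention), and their interaction", with a random intercept for provider. Section 9.4.2 (H1) has the two arm terms, year, and the effect under test, introduced "by interaction terms of study arm and year"; H2 uses the same strategy. For H3, section 9.4.3 says "This endpoint will be predicted by 2 fixed-effects terms for study arm of CDS (CDS vs. SP) and CDS-E (CDS-E vs. SP"), plus the provider intercept. H4 has the same structure as H3. Neither H3 nor H4 has a baseline period.

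Further covariates are planned but placed in another document. Section 9.4.1 says "Covariates to be included in models will be described in the Manual of Procedures (MOP"), and section 9.4.2 says "Additional covariates to be included will be described in the MOP". Matching statements appear for H3 and H4. The only covariates named anywhere are patient age, race and public pay status, in the sensitivity analyses of section 9.4.5.

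So the factors are sent to the SAP and the covariates to the MOP, and no sentence connects the two.

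**The concern.** Stratified allocation makes the arms more alike on the stratifying factors, which reduces the true sampling variance of the arm difference. A model without those factors does not know this. It counts the between-stratum differences as random provider variation and reports the variance of an unstratified design. The estimate keeps its balance, but the reported standard error does not reflect it, so intervals are too wide and the test rejects less often than its nominal 5%.

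This matters most where arms are compared between providers with no baseline to absorb provider differences, which is the structure of H3 and H4. H3 is a tested secondary hypothesis, and its information is limited by about 51 providers. H4 is descriptive, so only the width of its intervals is at stake.

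**Working it through.** **The plan's own figures.** Survey returns: 1,520 × 0.79 = 1,200.8, matching the stated 1,200 (section 9.2). The plan gives no power for H3 or H4. Its 80% belongs to H1. It reproduces as a comparison of post-period rates only: 6,900/51 = 135.3 patients per provider; design effect 1 + 134.3 × 0.3 = 41.3; effective n per arm 17 × 135.3/41.3 = 55.7; 38% against 15% then gives 79.4%. That figure is not carried over to H3, and no power change is claimed for H1.

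**Inputs for H3 and H4.**
- Surveys per provider: m = 1,200/51 = 23.5. Section 6.3 aims for roughly equal survey counts by provider.
- Survey ICC: not given; assumed 0.02 to 0.10, with 0.30 (the value stated for opioid use) as an upper case.
- Share f of between-provider variance explained by the strata: not given; assumed 0.1 to 0.5.

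**Formulas.** Per-provider variance, as a fraction of total variance:
- strata ignored: v0 = ICC + (1 − ICC)/m
- strata fitted: v1 = ICC(1 − f) + (1 − ICC)/m

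Under stratified allocation the estimate's true variance follows v1, so
- SE ratio (ignored/fitted) r = √(v0/v1)
- actual two-sided type I error when ignored = 2[1 − Φ(1.96 r)]

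Example, ICC 0.10 and f = 0.5: v0 = 0.10 + 0.90/23.5 = 0.138; v1 = 0.05 + 0.038 = 0.088; r = √(0.138/0.088) = 1.25; type I error = 2[1 − Φ(2.45)] = 1.4%.

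| Assumed ICC | r, f = 0.1 | Type I error | r, f = 0.5 | Type I error |
|---|---|---|---|---|
| 0.02 | 1.02 | 4.6% | 1.09 | 3.2% |
| 0.05 | 1.03 | 4.4% | 1.18 | 2.1% |
| 0.10 | 1.04 | 4.2% | 1.25 | 1.4% |
| 0.30 | 1.05 | 4.0% | 1.35 | 0.8% |

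**Check of the mechanism.** A simulation randomised 51 providers within three assumed strata and fitted random-intercept logistic models to one post-intervention period (135 patients per provider, latent ICC 0.3, 150 runs per setting). Mean model SE without and with strata was 0.396 and 0.337 at f = 0.25, and 0.401 and 0.276 at f = 0.50. The actual spread of the estimates did not change: 0.366 both ways, and 0.287 against 0.288. This uses a binary outcome and larger clusters than the survey, so it supports the mechanism and not the table's values.

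**H1 and H2.** The same simulation with two periods and the arm-by-period contrast gave a mean SE of 0.0963 without and with stratum main effects at f = 0.50, and 0.0965 both ways at f = 0.25 (ratio 1.000). The contrast is a within-provider change, so the provider intercept already absorbs a provider-level main effect.

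**The case against.** The strongest reply is that omission is not shown. Covariates are planned for every model and listed in the MOP, and the strata may be among them. This stands in part: the documents are silent on it, so the defect is a missing commitment and not a proven omission. Silence still leaves a reader unable to check that the analysis matches the randomisation.

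A second reply is that any error is conservative, affects one secondary test and one descriptive comparison, and may be small. That is also fair. At an ICC of 0.02 to 0.05 the excess in the SE is 2% to 18%, and with weak strata it is negligible.

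A reader might infer two stronger things, and neither is supported.
- *That the balance from stratifying is lost.* It is not. Balance comes from the allocation and stays in the estimate, as the unchanged spread in the simulation shows.
- *That the primary analysis also has inflated standard errors and gives away power.* The H1/H2 standard error does not change with stratum main effects. If strata or providers differ in their change over time, the error runs the other way, because the written model has no provider-by-period term. With an assumed slope SD of 0.5 logits, the model SE was 0.097 against an empirical SD of 0.194, and type I error was about 28% with or without stratum main effects. Where the strata themselves drive the change, stratum-by-period terms helped only slightly, for example from 11.2% to 8.5% rejection under the null. Describing H1 or H2 as conservative would therefore mislead.

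**Conclusion.** The point holds for H3 and H4 and not for H1 or H2. The plan stratifies the randomisation and commits no model to the strata. If they are left out, the H3 and H4 standard errors are about 2% to 25% too large, and the H3 test runs at about 4.6% down to 1.4% instead of 5%. At an ICC of 0.30 the excess could reach 35% and the type I error 0.8%. These sizes rest on the assumed ICC and share of variance explained, on 23.5 surveys per provider, and on allocation that balances the strata well. Validity is not threatened; precision is under-reported. Type I error applies to H3 only, since H4 is descriptive. The improvement is worth making because it is close to free.

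**What to change.** In sections 9.4.1 and 9.4.3, state that the H3 and H4 models include the randomisation stratification factors as fixed effects, and name those factors where section 6.3 says they will be named.

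The same factors can go into the H1 and H2 models, optionally with stratum-by-period terms. That is harmless and keeps the analysis consistent with the randomisation, but it brings little gain there and should not be presented as a gain in power.

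The cost is one sentence and a few provider-level degrees of freedom. The factors have to be recorded in order to randomise, so no new data are needed. The number of stratum terms should be kept small relative to 51 providers.

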6.4 STUDY INTERVENTION COMPLIANCE

The CDS is embedded into the existing EHR. CDS use will be documented to monitor fidelity in the intervention arms. Co-Investigators will regularly meet with study staff to discuss study progress and problem-solve potential issues. The purpose of these meetings is to focus on the day-to-day operations of the project (e.g., technical functionality) and to assure that all necessary tasks are completed in a timely fashion and strictly according to study protocol (e.g., integration into workflow and/or supplemental training). Quarterly meetings will include all co-investigators and will address any scientific issues (e.g., recruitment or enrollment) or safety issues (e.g., medication interactions) that may arise.

6.5 CONCOMITANT THERAPY

Not applicable

6.5.1 RESCUE MEDICINE

Not applicable

7 STUDY INTERVENTION DISCONTINUATION AND PARTICIPANT DISCONTINUATION/WITHDRAWAL

7.1 DISCONTINUATION OF STUDY INTERVENTION

Providers should exercise clinical judgment and can at their discretion disregard any information the CDS offers. As such, patients will receive usual dental care, regardless of study arm.

Hospitalizations documented within the HealthPartners electronic health record that occur within a 72-hour window following the index extraction encounter will be chart reviewed for severity and relatedness on a quarterly basis during the intervention period by Co-investigator and/or PI [name]. These hospitalizations rates will be compared at a frequency determined by the DSMB or quarterly whichever is greater.

Based on the relevant data, the study team in consultation with the DSMB would determine whether the study intervention needed to be modified or discontinued.

